Problem solving (PS) is an approach to behavior change that has a long history in the mental health literature (6), but is much less used, and less well tested, in the prevention arena. PS is an evolution of cognitive-behavioral therapy that addresses internal barriers to changing behavior, urging patients to use specific techniques designed to prime them for success in any behavior change they propose to attempt . PS is well-tested in mental health (6,7), and there are small studies suggesting its utility in changing behaviors associated with improved physical health (8,9). It is traditionally done in an individual setting, but recent literature indicates promise in use in group settings (10). However, PS has unproven effectiveness both in group settings, and among primary prevention patients.

Group visits have been shown to be an effective means of improving outcomes in a number of settings (11). Group visits can either involve medication management or be entirely focused on behavior change; self-management groups (SMGs) are behavior intervention groups that are conducted by a trained facilitator and focus on having patients teach each other how to adopt healthful behaviors (usually in chronic illness). Because there is no requirement for medication management, SMGs can be used efficiently in patients without medication-requiring chronic illness, as there is no attendant cost of employing a prescribing provider. SMGs can be used as a strategy to deliver a multifactorial behavior intervention in patients with a common illness (eg, 12-14). However, our study above (3) is the only RCT we can find of SMGs in primary prevention.

We therefore propose a **2-arm, parallel-group, patient-level randomization RCT** to evaluate the effectiveness of **Group Prevention Clinic (GPC)**, an SMG intervention intensified by problem solving theory, in reducing CVD risk among primary prevention patients with >5% 10-year risk for a cardiovascular event as estimated by the Framingham Risk Score (FRS). The study will be set in the Durham, Buffalo, and Syracuse VAMCs. VA usual care will be the control. The following are the specific aims:

Primary Specific Aim (Aim1): To determine the effectiveness of GPC, compared to VA usual care, in reducing CVD risk in a primary prevention population.

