Primary Hypothesis (H₁): Among patients with >5% 10-year risk for a cardiovascular event, there will be at least a 2.0% difference between GPC and usual care in reduction of predicted rate of fatal or non-fatal MI, as estimated by the Framingham Risk Score (FRS).

Aim 2: To determine the effectiveness of GPC (compared to VA usual care) in: (a) increasing physical activity, and (b) making dietary improvements.

H_{2A}: Compared to usual care, GPC will lead to an increase in physical activity as measured by International Physical Activity Questionnaire.

 H_{2B} : Compared to usual care, GPC will lead to a decrease in saturated fat intake, as measured by Food Frequency Questionnaire.

Aim 3: Among intervention patients, to determine the role of group cohesion in predicting the success (or lack thereof) of GPC.

H_{3A}: Strong group cohesion, as measured by the Group Cohesion Scale, will predict improvement in FRS among patients receiving the GPC intervention.

Aim 4 (exploratory): To measure the cost of the GPC intervention.

B. BACKGROUND AND RATIONALE.

B.1. Cardiovascular (CV) event prevention. Cardiovascular disease (e.g., myocardial infarction, cerebrovascular accident) remains the single most important public health problem in the United States (15), and cardiovascular disease is a leading cause of death among VA users (16). CV events are mostly considered preventable by more appropriate treatment of CV risk diseases (eg, hypertension (HTN) and hyperlipidemia (HL)). Modification of behavioral risk factors (eg, smoking cessation, increased physical activity, stress reduction) is also key to CV event prevention, both by direct effect on health as well as by improving the risk diseases above. Improving the provision of prevention services is a primary focus of the Secretary's New Models of Care Transformational Initiative (17). However, prevention of CV disease has been challenging to achieve, as can be seen by continued inadequate risk factor management; a fifth of Americans (a greater proportion of VA users) continue to smoke, only half of people achieve physical activity goals, and more than a third of VA users do not achieve treatment targets for blood pressure and/or cholesterol (18-21). The evaluation of alternative strategies to improve CV disease prevention is the focus of our CREATE.

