The phone interventionist will receive formal training in MI; we have purchased this service from a local MI teacher for numerous other personnel on other successful protocols (25). S/he will also receive training in coaching from professional coaches at Duke University Medical Center (3).

[name], who is the investigator with experience in problem solving (see budget justification for credentials) will supervise the interventionists. *To assure fidelity, all intervention group sessions and phone calls will be recorded, and those that are randomly chosen to be overheard by [name] will be overheard after they occur.* This eliminates a Hawthorn Effect for behavior of the interventionists when they know they are being observed. Second, we will establish checklists for both behaviors addressed and Problem-Solving approaches used in each session so we have a summative evaluation of intervention fidelity. **D.8. Measures.**

D.8.a. Primary Outcome Variable. The primary outcome is Framingham Risk Score, which yields a probability of major cardiovascular event over the next 10 years as its output (64). The inputs to FRS are: age; gender; diabetes status (which will be 0 at baseline for all enrolled patients); total and HDL cholesterol, which will be measured directly by standard VA laboratory methods; smoking status, measured by self-report; use of blood pressure medications, measured by VA medical record and self-report, and systolic blood pressure. All components of the FRS will be measured at each study visit. At each visit, two measurements of blood pressure, taken seated after a 5-minute rest and at 5-minute intervals, will be obtained. The final outcome will be the average of the two measures. All BP measurements will be performed using electronic blood pressure cuffs (148). Study personnel will be trained in measurement technique using established methods (149).

D.8.a.i. Justification for primary outcome. Patients in the intervention arm may choose one of a number of behaviors to work on, with no obvious common outcome across all potential behaviors (for example, someone who quits smoking has probably improved her/his cardiovascular risk even if s/he gains 10 pounds). Thus, a direct measure of risk is needed, and FRS is the best validated of these. Also, we have experience with successfully improving FRS in coaching interventions (3).

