 $Y_{ijt} = \beta_0 + \beta_1 int^* month6 + \beta_2 month12 + \beta_3 int^* month12 + \beta_4 site + \beta_5 gender + \beta_6 smoking + c_j int^* month6,$

where Y_{ijt} is Framingham risk score for subject *i* in group *j* at *t*=month0, month6. We will estimate the parameters in the model using the SAS procedure MIXED (Cary, NC), and we will test to see if there is a difference in mean FRS change at month 6 between the GPC and usual care arm, i.e., $\beta_1 < 0$. The way time is coded in this model is often referred to as a constrained longitudinal data model (cLDA) (87) in which the month 0 risk is modeled as a dependent variable in conjunction with the constraint of a common month0 mean across the treatment arms. In this way, the cLDA model is comparable to an ANCOVA model; the two models are equivalent when there is no missing data. However, unlike an ANCOVA, subjects who are missing the month 6 measurement are included in the model because baseline is part of the response vector. As recommended by the CPMP (80), the model will also be adjusted for stratification variables of site, gender, and smoking status for improvement in precision. We will use an unstructured covariance to account for the correlation between repeated measurements, and we include a group-level random effect for intervention arm

patients, c_i, to account for the intra-class correlation between patients in the same prevention group. Similar procedures will be used to assess change through month 12 as a secondary analysis.

D.9.e. Aim 2 Analyses. Similar to the FRS, the secondary outcomes are all continuous and measured at baseline, month 6, and month 12. Analyses of these outcomes will thus proceed as describe above for FRS.

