D.9.f. Aim 3 Analyses. The analyses for Aim 3 will only include the intervention arm patients and will be exploratory in nature. The primary outcome for these analyses will be change in FRS from baseline to month 6. We will consider multiple ways of characterizing group cohesion, including: each individual's group cohesion score at the last group session; each individual's change in group cohesion from the first to the last group session; and, the mean group cohesion score at the last group session will be examined with a linear mixed-effects model, where additional predictors will include gender, smoking status, site, race, and age. A random effect for group membership will be included in the model to account for the intra-class correlation between patients in the same prevention group. Because the main predictors in these analyses are measured throughout the intervention, these analyses may be more impacted by drop-out or missed interim assessments than the Aim 1 and 2 analyses. We plan to use multiple imputation as the primary approach for handling missing data for the Aim 3 analyses.

D.9.e. Sample Size Calculations. The primary aim is to determine if there is a significant GPC vs usual care improvement in the mean FRS change from baseline to month 6. The clinically relevant mean FRS change is 2.0%. We assumed that FRS is normally distributed, and set the type-I error rate at α = 0.05 and the

type-II error rate at β = 0.20, representing power at 80% to detect significant differences. To take the intra-class correlation (ICC) among the group members in the GPC into consideration, we

applied the sample size procedures for group-randomized designs of Donner and Klar (88). Let *m* be the number of participants in each of the prevention coaching groups, and let ρ represent the ICC among the members of the group. In general, the minimum number of participants in each treatment arm is given by, $n = (Z_{1-\alpha/2} + Z_{1-\beta})^2 (2\sigma^2) [1 + (m-1)\rho] / (\mu_{GPC} - \mu_{UC})^2.$

Here, Z_p is the *p*-th percentile from the standard normal distribution, while μ_{GPC} and μ_{UC} is the anticipated mean change for the GPC and usual care arms, respectively. However, this formula is not quite right for this study – the control condition is usual care, and no ICC is anticipated among its members. As a result, the formula is modified to,

 $n = (Z1 - \alpha/2 + Z1 - \beta)^2 \{\sigma^2 + \sigma^2 [1 + (m - 1)\rho]\} / (\mu 1 - \mu 2)^2.$

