The first σ^2 in the braces corresponds to the variance for the usual care control group, while the $\sigma^2[1 + (m-1)\rho]$ incorporates the design effect in GPC intervention arm (only).

The anticipated SD of the change in FRS was derived from previous studies, with a value of 6.3%. We have observed a baseline mean of 29% (SD = 14%) and a correlation between 6 month intervals of 0.9 (3). With respect to p, we have observed values in the previous studies of 0.03 (11). Finally, we took m = 10 as the average size of the prevention coaching groups.

Applying these assumptions results in a sample size of 180 per arm, or n=360 patients total. We further inflate the sample size to account for a possible 10% attrition rate by the 6-month follow up. Therefore, we plan to enroll n=400 patients total to detect a 2.0% between-arm difference in the change from baseline to month with 80% power and a type-I error of 5%.

D.10. DATA MANAGEMENT AND QUALITY CONTROL

D.10.a. Data Management Procedures. We will use a series of asynchronously connected database applications, over which a comprehensive data model will be deployed. Each database application will function independently as a discrete system. All data transactions within and between subsystems will run through secure transactions to ensure database integrity and privacy. Study data will be maintained on secure servers for the duration of the study and as long after the completion of the study as required by VA regulations at the time of study closure. All study data will be backed up on a nightly, monthly, and annual schedule.

All server hardware has built-in redundant systems. Technicians will constantly monitor server hardware, operating system and database service performance. Workstations, laptops, and any other devices will be supported in order to ensure high performance and secure operation. The primary database technology will be Microsoft SQL Server. All automated systems will run using the Microsoft SQL Server Management Agent. Automated processes will be monitored daily. The system will be configured to notify the HSR&D IT Group if an automated process fails to run successfully. The data collected during in-person interviews will be entered directly into our third party survey application named "DatStat Illume" running on an encrypted, password-protected laptop (www.datstat.com/). This survey application has been developed using Microsoft Visual

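### Does H1's wording of at least 2.0%, with the direction of the test written two ways, leave a positive result undefined?

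*Combined protocol and SAP*

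**What the plan says.** - **Section A, H1.** The hypothesis is that "there will be at least a 2.0% difference between GPC and usual care in reduction of predicted rate of fatal or non-fatal MI". It names no time point.
- **D.9.d, Primary Analysis.** The analysts state that "we will test to see if there is a difference in mean FRS change at month 6 between the GPC and usual care arm", and follow this at once with the inequality beta1 < 0. The section contains no 2.0-point margin and no alpha.
- **D.9.e, Sample Size Calculations.** The aim is to find "a significant GPC vs usual care improvement in the mean FRS change" from baseline to month 6. Alpha is set at 0.05, and both the general and the modified formula use Z at 1 - alpha/2. The role of 2.0 is given twice: "The clinically relevant mean FRS change is 2.0" percent, and 400 patients are to be enrolled "to detect a 2.0% between-arm difference in the change from baseline to month with 80% power and a type-I error of 5" percent. The size before attrition is also stated: "Applying these assumptions results in a sample size of 180 per arm".
- **Event predicted by the score.** H1 speaks of MI. The design paragraph of section A describes patients "with >5% 10-year risk for a cardiovascular event as estimated by the Framingham Risk Score (FRS"), and D.8.a says of the score, "which yields a probability of major cardiovascular event over the next 10 years as its output".

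**The concern.** Three things catch the eye.

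First, rejecting zero does not show a difference of at least 2.0 points. Read strictly, H1 and the primary test answer different questions, and the plan does not say how to describe a significant estimate below 2.0.

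Second, D.9.d says difference but writes a directional inequality, while the sample size section says improvement but uses a two-sided critical value. If someone put the whole 5% in one tail, an estimate between about 1.16 and 1.39 points would be positive under one reading and negative under the other.

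Third, H1 labels the outcome as MI, whereas other sections label it as cardiovascular events.

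The stake is the verdict of the trial. Sections C and E tie rapid implementation across VA to the intervention being effective, so the meaning of effective ought to be settled before results are seen.

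**Working it through.** **Inputs (D.9.e, Sample Size Calculations).** SD of change 6.3 points; ICC 0.03, in the GPC arm only; group size m = 10; difference 2.0 points; alpha 0.05; power 80%; attrition 10%.

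**Step 1: reproduce the stated size.** The variance factor is 1 + [1 + (10 - 1) × 0.03] = 2.27.

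- Two-sided: n = (1.960 + 0.8416)² × 6.3² × 2.27 / 2.0² = 176.8, so 177 per arm. This is within 3% of the stated 180.
- One-sided 5%: n = (1.645 + 0.8416)² × 6.3² × 2.27 / 2.0² = 139.3, so 140 per arm. This is nowhere near 180.
- Attrition: 360 / 0.9 = 400, as stated.

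The stated size therefore belongs to a two-sided 5% test of zero, with 2.0 as the alternative.

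**Step 2: what that test does at 180 per arm.** SE = √(6.3² × 2.27 / 180) = 0.7075.

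- Smallest significant estimate: 1.960 × 0.7075 = 1.387 points.
- Power at a true 2.0: Φ(2.0/0.7075 - 1.960) = Φ(0.867) = 0.807.

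**Step 3: where the ambiguous zone comes from.** Its lower end is 1.645 × 0.7075 = 1.164. The value 1.645 is Z at 1 - alpha, which appears nowhere in the document. Combining the direction in D.9.d with the critical value in D.9.e means rejecting in favour of beta1 < 0 when the estimate passes 1.960 standard errors. The threshold for benefit is then 1.387 points whether the test is described as a difference or as an improvement. The one-sided figures (140 per arm, and power of Φ(2.827 - 1.645) = 0.881) need the same absent cutoff.

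**Step 4: could 2.0 have been meant as a margin?** For a test that the difference exceeds 2.0, the denominator of the formula becomes (true difference - 2.0)². At the plan's own planning value of 2.0 this is zero, so no sample size would serve. The required estimate would be 2.0 + 1.387 = 3.387 points, and the chance of reaching it at a true 2.0 would be 2.5% by construction. A plan that claims 80% power at 2.0 is not using 2.0 as a margin.

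**Step 5: significant estimates below 2.0.** If the truth is exactly 2.0, half of all estimates fall above it. The chance of a significant estimate below 2.0 is therefore 0.807 - 0.500 = 0.307. This is power minus one half, so any trial with about 80% power at its design difference shows about 30%. It does not point to a defect in this plan.

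**Step 6: sensitivity to the planned model.** With the baseline SD of 14 and correlation of 0.9 from the same section, the residual SD is 14 × √(1 - 0.9²) = 6.10. With the same design effect, SE = √(6.10² × 2.27 / 180) = 0.685 and the two-sided threshold is 1.343. The picture is the same.

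**Step 7: the label.** D.3.a and D.8.a cite the same source for the score (reference 64) and list the same inputs. The label does not enter the calculation of the outcome.

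**The case for a change.** The strongest reply is that a reader has to infer all this. D.9.d is the section an analyst follows, and it gives neither an alpha nor a number of sides; these must be taken from the sample size section. H1 does say at least, and someone could later argue either that a significant estimate of 1.5 confirms it or that it does not. With implementation depending on the answer, a few words would remove the argument at no cost in patients or analyses. It can be added that the Aim 2 analyses are to proceed as for FRS, where H2A predicts an increase in physical activity; beta1 < 0 used there as a rejection rule would point the wrong way.

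Part of this stands. The wording is loose, the sides of the test are never named, and H1 read literally is not what is tested. But the inference is short, and only one critical value is available to make it with. The Aim 2 point favours the benign reading: the inequality makes sense only as the expected sign for FRS, where lower is better, and not as a general decision rule. H1 sits among the specific aims as a prediction, and D.3.b explains that 2% is roughly the effect seen in the group's earlier study of a similar intervention. No part of the plan says that significance will be reported as proof of at least 2.0 points.

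**Conclusion.** No change to the plan is called for. Followed as written, it yields a two-sided 5% test of the month-6 difference against zero, with 2.0 points as the planning difference. At 180 analysed per arm the smallest significant estimate is about 1.39 points (1.34 allowing for the baseline correlation), and power at a true 2.0 is 81%. The sample size of 180 per arm, or 400 with attrition, is sound on the plan's inputs.

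The missing word two-sided is a gap that any analyst would fill the same way. The phrase at least in H1 is an optimistic prediction, not a test criterion. The MI and cardiovascular-event labels are a clerical mismatch; the document does not show which one fits the score version used, and neither choice alters a number.

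This rests on two assumptions: that the critical value used for planning is also the one used for testing, and that beta1 is the month-6 arm difference, as the text of D.9.d says. The primary result would have to be read as evidence of a difference from zero, and its size judged from the estimate and its interval. That is ordinary reporting and needs no new rule.
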